## **Justification for the Project**

Obesity in adolescence is associated with physical and mental health problems and predicts obesity in adulthood. Adolescence may be an ideal time to target interventions, as this is when numerous health-related habits are consolidated (Bryan et al., 2019). Several universal preventive interventions have been carried out in educational centers for the promotion of healthy eating habits. However, the results of reviews and meta-analyses have concluded that most are not cost-effective for producing long-term changes in the dietary preferences of young people (Ashton et al., 2019; Kobes et al., 2018).

### **Why Do Traditional Interventions with Adolescents Fail?**

Traditional interventions typically include nutrition education strategies and tell adolescents what behaviors they should and should not engage in (Steinberg, 2015). However, some characteristics of adolescence can cause these approaches to fail. If adolescents perceive that adults are trying to manipulate them or introduce behavioral patterns such that their autonomy is threatened, they will often resist (Yeager et al., 2018).

The so-called wise interventions paradigm is an innovative approach to interventions that involve a set of rigorous techniques grounded in research to help people improve in a variety of life settings (Walton & Wilson, 2018). In recent years, a proliferation of wise interventions has achieved significant results in addressing social and personal problems, such as depression, stress, and other health problems. Furthermore, this type of intervention is of great interest to adolescents as it is designed in a way that is perceived as respectful of adolescents' autonomy and status (Yeager et al., 2018).

Recently, Bryan et al. (2016, 2019) developed a wise intervention aimed at improving adolescents' daily dietary choices. Their intervention, called the values alignment intervention, focused on the role of marketing on the behavior of children and adolescents who are exposed to a relentless barrage of marketing from the food industry. This marketing strategy is designed to reinforce the positive value of junk food and increase its consumption. Therefore, many experts have pointed to marketing as a key risk factor for unhealthy eating in the general population (Harris et al., 2009).

The values alignment intervention seeks to neutralize the positive emotional associations with junk food that marketing generates and presents the rejection of unhealthy foods in favor of healthy alternatives as a way to live up to two values that are important to adolescents: (1) the desire to be autonomous from adult control, and (2) the desire for social justice (Bryan et al., 2019). In two randomized controlled trials, this team demonstrated that the intervention reduced implicit positive associations with junk food and substantially improved dietary choices, especially in boys (Bryan et al., 2016, 2019). In addition, there were significant differences in attitudinal variables related to healthy eating. These promising results suggest that reframing unhealthy eating as incompatible with important youth values could be a low-cost solution to produce changes in adolescent attitudes and dietary choices.

## **Project Objectives**

The general objective of this project is to adapt the values alignment intervention to improve obesity-related eating habits in Spanish adolescents. It is therefore a highly innovative project with great potential for social impact in the field of health promotion. The specific objectives

are: (1) to adapt the values alignment intervention to the Spanish culture and context, (2) to evaluate the effects of the intervention in reducing unhealthy food intake and increasing healthy food intake in adolescents, (3) to evaluate differences between adolescents receiving the intervention and those in the control group regarding attitudinal variables related to healthy eating (alignment of healthy eating habits with adolescents' values and social attractiveness of healthy eating), (4) to evaluate potential moderators of the effect of the intervention, specifically socioeconomic status, given that more disadvantaged socioeconomic levels are associated with worse eating habits and greater obesity, gender, given that in the study by Bryan et al. (2019) the effect was more beneficial in boys, and body mass index (BMI), given that those adolescents with a higher BMI may present more consolidated habits of unhealthy food consumption, and (6) to evaluate whether the effect of the intervention on eating behavior is mediated by attitudinal variables.

## **Methodology**

**Sample:** The study will be carried out with adolescents in the second and third years of high school in Bizkaia (Spain). The necessary estimated sample size is 500, under a small, anticipated effect size (0.2), a statistical power of 0.8, and a probability level of 0.05. In anticipation of a loss of participants during the follow-ups, the sample size will be increased to 600. Inclusion criteria include adequate reading comprehension and parental and self-informed consent.

**Design and Procedure:** A randomized controlled trial with two groups will be used. Randomization will be done by clusters, using the classroom as the unit. First, the schools will be selected according to their characteristics. Then, for each school and grade, half of the classrooms will be randomly assigned to the experimental condition (values alignment) and the other half to the control condition (traditional educational intervention). Participants will complete an online assessment protocol using Qualtrics, which will be composed of different questionnaires at three time points: (1) pretest (immediately before the intervention), (2) posttest (one week after the intervention), and (3) a three-month follow-up. The study has the approval of the Ethics Committee of the University of Deusto. The trial will be registered on ClinicalTrials.gov.

**Interventions:** The experimental group will receive the values alignment intervention (Bryan et al., 2016). This includes: (1) reading materials, such as recent journalistic works that expose the deceptive and manipulative marketing practices of food companies and the harmful effects of these practices on society, with particular emphasis on harm to young children and the economically disadvantaged. Stories from other young people will also be included in order to contribute to the perception of widespread outrage and to suggest how that outrage can be channeled into taking a stand against the injustice perpetrated by food companies by eating less unhealthy or healthier food, (2) writing exercises, such as a story with a brief statement of what the participants would tell a younger child about the ads, and (3) an interactive activity, called "Make It Real" in which they are shown pictures of food ads and allowed to write and draw about them, making whatever changes (e.g., crossing out and substituting words) they feel necessary to make the ad "real" (i.e., no longer misleading). The control group will receive a traditional educational intervention on nutrition and physical exercise. This will be of the same duration and will also include reading and writing exercises.

**Measurements:** Healthy and unhealthy food intake will be measured at pretest, posttest, and three-month follow-up using the questionnaire developed by Stok et al. (2015). It consists of

four items that provide an index of unhealthy eating. In addition, according to the content addressed in the intervention sessions in the posttest and three-month follow-up, two attitudinal variables will be evaluated: (1) the alignment of healthy eating habits with the values of adolescents using seven items from Bryan et al. (2019), and (2) the social attractiveness of healthy eating using three items from Bryan et al. (2019), and answered on a five-point scale. Finally, some individual characteristics will be measured through an ad hoc questionnaire: gender, age, socioeconomic status (education and parental profession), height, and weight (to determine BMI).

**Statistical Analysis:** To evaluate the effect of the intervention on the repeated measures of the dependent variables, a multilevel analysis with MPLUS-8.8 will be used. This will include repeated measures at level one (e.g., healthy and unhealthy food intake), adolescent variables at level two (assigned intervention and potential moderators), and the classroom at level three. It will be determined whether the intervention explains the slope of change of the dependent variables (intervention  $\times$  time interaction). For moderation effects, triple interaction terms will be created using dummy variables or z variables, depending on the nature of the variables. To assess whether the effect of the intervention on healthy and unhealthy food intake is mediated by the attitudinal variables, a structural equation model with a bootstrapping procedure will be estimated ( $N = 10,000$  samples). For the handling of missing values, the full information maximum likelihood method will be used as a general approach, although, depending on the nature of the missing value patterns, other techniques (e.g., multiple imputations or use of auxiliary variables) may be used.

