#### BUDGET

Concept	Amount
Contract for a research assistant with a degree in psychology on a part-time basis (25 hours per week).	20,000
Travel and per diem expenses for researchers [name] and [name] for coordination and adaptation of the intervention materials for Spanish adolescents.	6,100
Incentive vouchers for participants. Vouchers will be raffled among the participants in each classroom to encourage participation. These will have a value of 20 euros and can be exchanged in shopping centers. Two vouchers will be raffled in each of the approximately 30 classrooms.	1,200
Trips to schools.	1,100
Expendable materials, such as markers and paints for intervention activities, which will be given to the adolescents.	1,600
Total	30,000
QUARTERLY WORK PLAN	1 2 3 4
1. Adaptation of the materials for Spanish adolescents	x
2. Acquisition of materials	x
3. Training the research staff on the procedures	x
4. Contacting schools and obtaining permissions	x
5. Application of pretest and intervention measures	x x x
6. One-week and three-month follow-ups	x x
7. Merging and cleaning of databases	x
8. Statistical analysis of data	x x
9. Writing the final report and scientific manuscripts	x
10. Dissemination and transference in conferences, participating schools, and society in general	x

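### The claim that 500 participants give 80% power at an effect size of 0.2 does not follow from the stated inputs (about 788 two-sided, 620 one-sided), and no allowance for classroom randomisation is documented

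*Combined protocol and SAP*

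**What the plan says.** The Sample paragraph of the Methodology gives the whole sample size justification: "The necessary estimated sample size is 500, under a small, anticipated effect size (0.2), a statistical power of 0.8", with a probability level of 0.05. It then adds: "In anticipation of a loss of participants during the follow-ups, the sample size will be increased to 600". It does not name a test, an effect-size metric, sidedness, a within-person correlation, an ICC, a design effect or a dropout rate.

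Three other places bear on it:

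- Design and Procedure: "Randomization will be done by clusters, using the classroom as the unit". Within each school and grade, half the classrooms go to each arm. There are three assessments: pretest, one week and three months.
- Statistical Analysis: a three-level model with the classroom at the top level. On the effect of interest it says: "It will be determined whether the intervention explains the slope of change of the dependent variables".
- Budget: "Two vouchers will be raffled in each of the approximately 30 classrooms". This is the only indication of the number of clusters.

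**The concern.** An effect size of 0.2 described as small, with 80% power and 0.05, is the familiar specification for a two-group standardised mean difference, and that calculation gives a total well above 500. The increase to 600 cannot make up the difference, because it is already committed to losses. Randomising classrooms inflates the variance of the treatment comparison, which pushes the requirement up further. Repeated measures can pull it down, but by an amount that depends on inputs the plan does not give.

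The Sample paragraph is the only statement of what the trial can detect. If it is unsupported, a reader of a null result cannot tell from the plan whether an effect of 0.2 was within reach.

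**Working it through.** **Inputs from the plan.** Effect 0.2, power 0.80, alpha 0.05, two equal arms, N = 500 (600 enrolled), about 30 classrooms. **Assumed, because the plan is silent:** 0.2 is in SD units; ICC is 0.01, 0.02 or 0.05; the correlation r between any two occasions is equal, with 0.6 as the worked value.

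**Step 1. Trying to reproduce 500.** Per arm, n = 2(z_alpha + z_power)² / d².

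- Two-sided: 2(1.960 + 0.842)² / 0.04 gives 393 per arm, 786 in total. The exact t-test gives 393.4 per arm, so 788.
- One-sided: 2(1.645 + 0.842)² / 0.04 gives 310 per arm, 620 in total. The exact t-test gives 309.8 per arm, so again 620.
- Other readings of 0.2: paired comparison about 199, Cohen's f 198, correlation about 194.

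None gives 500. By t-test, power at d = 0.2 is 0.607 two-sided (0.722 one-sided) with 500, and 0.686 (0.789) with 600. With 500, two-sided power of 80% corresponds to d of about 0.25.

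**Step 2. Adding an unstated input.** Adjusting one follow-up for baseline multiplies N by 1 − r²: 786 × (1 − 0.36) = 503 at r = 0.6. Averaging three measures multiplies it by (1 + 2r)/3: 786 × 1.9/3 = 498 at r = 0.45. Both land near 500, but neither includes clustering and neither is the slope test in Statistical Analysis.

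**Step 3. Adding the classrooms.** SE = √(4 × DE × VF / N), with DE = 1 + (m − 1) × ICC and power from the non-central t on 30 − 2 = 28 df. VF is the variance factor of the quantity tested, and the ICC is applied to that quantity. With N = 500, m = 500/30 = 16.7 and DE = 1.157, 1.313 and 1.783.

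Power at 0.2, two-sided, r = 0.6 where r applies:

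| Quantity tested | VF | N | ICC 0.01 | ICC 0.02 | ICC 0.05 |
|---|---|---|---|---|---|
| Unadjusted difference | 1 | 500 | 52% | 47% | 37% |
| Pre-to-last change | 2(1 − r) = 0.80 | 500 | 61% | 56% | 44% |
| Pre-to-last change | 0.80 | 600 | 68% | 61% | 47% |
| One baseline-adjusted follow-up | 1 − r² = 0.64 | 500 | 71% | 65% | 52% |
| Baseline-adjusted mean of both follow-ups | (1 + r)/2 − r² = 0.44 | 500 | 86% | 81% | 68% |

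With time coded 0/1/2, the slope test has the same power as the pre-to-last change, so those rows are closest to the planned analysis. Coding matters. In weeks (0/1/13) at r = 0.6 with 500, power is 70% / 65% / 52% if the effect grows linearly to 0.2, and 30% / 27% / 21% if 0.2 is present at posttest and simply held.

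**Step 4. Correlation needed for the change to reach 80%.** With 500 and no clustering, r = 1 − 500/(2 × 786) = 0.68. With clustering, r = 0.74 / 0.77 / 0.83 at the three ICCs. If all 600 are analysed, r = 0.70 / 0.74 / 0.82.

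**The case against.** The plan does not call 0.2 a Cohen's d and does not plan a single post-only comparison, so 788 and 620 are benchmarks for an analysis that the trial will not run. A baseline correlation of about 0.6 recovers 500, so failure to reproduce the figure does not prove it wrong. The clustered powers depend on assumed values. With 600 analysed and r = 0.75, the change reaches 86% / 81% / 67%, and full information maximum likelihood puts the effective N between 500 and 600. Allocation within school and grade may lower the ICC if it is modelled. The 30 classrooms come from a raffle budget line, and the time coding is not given. The analysis itself includes the classroom level, so its validity is not in question, and confidence intervals would still show which effects are excluded.

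Most of this stands as a limit on what can be said: the trial's true power is unknown, and the tabulated percentages are illustrations. It does not rescue the stated claim. Each route to 500 needs an input that the plan omits, leaves out clustering, and belongs to a different test from the planned one. The favourable case, a baseline-adjusted mean of both follow-ups, is likewise not the analysis described. Baseline adjustment is also not evident for the two attitudinal outcomes, which the Measurements paragraph places only at posttest and follow-up.

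**Conclusion.** The concern holds and should be corrected before the plan is relied on. As a two-group standardised difference, the stated inputs need 788 (two-sided) or 620 (one-sided), against 500. Even the full 600 falls short of 80% under either sidedness, with no dropout and no clustering. That part rests only on reading 0.2 as a standardised mean difference.

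For the planned intervention-by-time test in about 30 classrooms, power is below 80% at r = 0.6 for every ICC considered, whether 500 or 600 are analysed. It reaches 80% only if r is about 0.70 or higher, and considerably higher at the larger ICC. This part rests on the assumed r, ICC, equal correlations and 0/1/2 time coding. The defect is confined to planning; the multilevel analysis does account for classrooms.

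**What to change.** Keep enrolment at 600. Redo the calculation for the intervention-by-time test, stating the effect metric, sidedness, time coding, number and size of classrooms, ICC, within-person correlation and expected loss. If the existing calculation already used such values, report them. Show the result over a range of ICC and correlation, and replace the present claim with the resulting power or detectable effect.

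For orientation, with 500 analysed in about 30 classrooms at ICC 0.01 to 0.05, the effect detectable with 80% power is about:

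- 0.28 to 0.35 SD unadjusted;
- 0.25 to 0.31 SD for a pre-to-last change at r = 0.6;
- 0.22 to 0.28 SD for one baseline-adjusted follow-up at r = 0.6.

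The cost is one recalculation and one rewritten sentence, with no extra participants. The downside is that the published sensitivity will probably look less favourable than 80% at 0.2.

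### Objective 2 and the analyses treat healthy intake as an outcome, but the only intake score the plan defines is a four-item unhealthy-eating index

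*Combined protocol and SAP*

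**What the plan says.** Under Project Objectives, objective 2 is to evaluate the intervention's effects in "reducing unhealthy food intake and increasing healthy food intake in adolescents". These are two effects on two quantities.

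Under Methodology, the Measurements paragraph states that "Healthy and unhealthy food intake will be measured at pretest, posttest, and three-month follow-up", using one cited questionnaire. The next sentence describes that questionnaire as "four items that provide an index of unhealthy eating". The rest of the paragraph lists two attitudinal variables, assessed at posttest and three-month follow-up, and then says that "some individual characteristics will be measured through an ad hoc questionnaire". Those characteristics are demographic details, plus height and weight to derive BMI.

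Also under Methodology, the Statistical Analysis paragraph places "repeated measures at level one (e.g., healthy and unhealthy food intake" in the multilevel model. It later plans a structural equation model to assess whether "the effect of the intervention on healthy and unhealthy food intake is mediated by the attitudinal variables".

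**The concern.** The objective and the analyses need a measure of healthy intake. The measurement text first says there is one, and then defines a score that runs in one direction and is named for unhealthy eating only. No healthy-intake score, subscale or second intake instrument is described.

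Intake is the trial's behavioural outcome, and the moderation and mediation objectives build on the effect on it. If the index is analysed as described, half of objective 2 and the healthy-intake part of the mediation analysis have no defined outcome. A reader of a favourable result could not tell whether adolescents ate less unhealthy food, more healthy food, or both. Because item content and scoring are not stated, the choice between one combined index and two scores also stays open until after the data are seen.

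**Working it through.** The plan gives no figure to reproduce on this point. The check sets the passages side by side and then asks what an index can show.

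**Step 1: what is needed and what is defined.**

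| Place | Healthy intake | Unhealthy intake |
|---|---|---|
| Project Objectives, objective 2 | to increase | to decrease |
| Measurements, first sentence | said to be measured at three waves | said to be measured at three waves |
| Measurements, description of the score | no score defined | four-item index |
| Measurements, remaining variables | none concerns intake | none concerns intake |
| Statistical Analysis, multilevel model | named as an example outcome | named as an example outcome |
| Statistical Analysis, mediation model | named as an outcome | named as an outcome |

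The left-hand column has a gap exactly where the score should be defined.

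**Step 2: what the index can show.** Item content and scoring are not in the documents, so each case is taken in turn.

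*Case A: all four items are unhealthy foods.* Healthy intake does not enter the index, which therefore carries no direct information on it.

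*Case B: some items are healthy foods, reverse-scored into the index (an assumption for illustration).* Let U be the sum of the unhealthy items and H the sum of the healthy items. Apart from a constant, the index sum is I = U − H, so the change is ΔI = ΔU − ΔH. Three patterns give the same result:

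| ΔU | ΔH | ΔI = ΔU − ΔH | Healthy intake |
|---|---|---|---|
| −1 | 0 | −1 − 0 = −1 | unchanged |
| 0 | +1 | 0 − 1 = −1 | higher |
| −2 | −1 | −2 − (−1) = −1 | lower |

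This does not depend on how the four items split, as long as there is at least one of each kind. The same subtraction applies to between-group differences in change. An intervention effect on the index is the effect on U minus the effect on H, and one number does not determine both.

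*Case C: some items are healthy foods and are scored separately.* Objective 2 could then be addressed in full, but the plan describes no such score.

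**Step 3: result.** In cases A and B the index leaves the healthy-intake half of objective 2 unanswered. Only case C answers it, and that scoring is not in the plan.

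**The case against.** The strongest reply is that the sentence about the index is a loose summary. The sentence before it says the questionnaire measures both kinds of intake, and the Statistical Analysis paragraph twice treats both as outcomes. Nothing says the index is the only score to be used. If the questionnaire has healthy-food items, the item-level data could answer objective 2 with no change in design.

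This stands as a limit on the conclusion. A reader might infer that the trial cannot measure healthy intake at all. The documents do not support that, because they do not show the items. The impossibility attaches to the index, not to the item-level data. The reply does not remove the disagreement, however: a score that the analysis needs is not defined anywhere.

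A reader might also take the phrase "whether the intervention explains the slope of change of the dependent variables" as evidence of two intake outcomes because of its plural. It is not, since the attitudinal variables are also measured more than once and explain the plural equally well. The point rests on the two explicit mentions of both intakes. The first is only given as an example, but the mediation sentence carries no such qualifier.

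It can fairly be said that the arithmetic is an identity and not an estimate of bias in this trial. That is correct; it shows only what an index can and cannot separate.

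Lost text is not a likely explanation. The sentence describing the four items runs across a break but reads as complete, and there is no sign of redaction.

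**Conclusion.** The inconsistency is established from the text: Project Objectives and the Statistical Analysis paragraph require healthy intake as an outcome, and the Measurements paragraph defines only an unhealthy-eating index. Confidence in this is high.

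The consequence is conditional. If the index is the score analysed, no separate conclusion about healthy intake is possible, whether the items are all unhealthy foods or include reverse-scored healthy ones. If healthy items exist and are scored on their own, the objective can be met, but the plan must say so. The size is half of objective 2 and the corresponding part of the mediation analysis; no numerical bias can be attached to it.

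A reader might go further and infer an inflated error rate or a larger required sample from having two intake outcomes. The documents do not support a figure. Objective 2 joins its two aims with a conjunction, so it is not given that success on either would suffice, and the plan states no success rule. This should be settled before pretest, because items not asked at baseline cannot be recovered later.

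**What to change.** Before pretest, state the content and scoring of the four items and reconcile the three places in the plan. Then:

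- **If the items include healthy foods:** define separate healthy and unhealthy intake scores, with items, scoring and direction, and analyse both at all three waves.
- **If they do not:** either add a few healthy-food frequency items to the online questionnaire at all three waves, or restrict objective 2 and the multilevel and mediation analyses to the unhealthy-eating index and draw no conclusion on healthy intake.

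If two intake outcomes are kept, state whether both must succeed or which one is primary. Requiring both needs no split of the significance level, but power for the joint claim is lower than for either alone. Naming one as primary leaves the other without a confirmatory test.

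The costs are small. Separate scores built from so few items are less reliable than the full index. Added items would come from outside the cited questionnaire and lengthen each assessment slightly. The restricted option changes only wording, but it narrows what the trial can claim.

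### If the two attitude outcomes are measured only after the intervention, the one effect test the plan names (intervention × time) measures persistence, not the group difference in objective 3

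*Combined protocol and SAP*

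**What the plan says.** All passages are in the combined protocol and SAP.

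- **Objective 3 (Project Objectives):** "to evaluate differences between adolescents receiving the intervention and those in the control group regarding attitudinal variables related to healthy eating". The quantity sought is a between-group difference.
- **Waves for intake (Methodology, Measurements):** "Healthy and unhealthy food intake will be measured at pretest, posttest, and three-month follow-up".
- **Waves for attitudes (same paragraph):** "according to the content addressed in the intervention sessions in the posttest and three-month follow-up, two attitudinal variables will be evaluated". The two variables are the alignment of healthy eating with adolescents' values and the social attractiveness of healthy eating.
- **Assessment schedule (Methodology, Design and Procedure):** one online protocol, "which will be composed of different questionnaires at three time points". The posttest is one week after the intervention, so both waves named for attitudes come after it. No scale is assigned to a wave here.
- **Effect test (Methodology, Statistical Analysis):** the multilevel model has "repeated measures at level one (e.g., healthy and unhealthy food intake") and "adolescent variables at level two (assigned intervention and potential moderators"), with the classroom at level three. The test is "whether the intervention explains the slope of change of the dependent variables", that is, the intervention × time interaction.
- **Mediation (same paragraph):** whether the intake effect "is mediated by the attitudinal variables, a structural equation model with a bootstrapping procedure will be estimated".

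No separate analysis is named for the attitude outcomes, and the coding of time is not stated.

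**The concern.** A group-by-time interaction tests a treatment effect when the first wave precedes treatment. The groups then start level in expectation, and a difference in slope is the effect. Intake has such a wave. On the natural reading, attitudes do not: the first attitude measurement already contains whatever the intervention has done, and the interaction subtracts it.

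An analyst who applies the named test to attitudes could therefore report no effect on both outcomes when the intervention had shifted them and the shift had lasted. A benefit that partly fades would give a coefficient pointing against the intervention, although pupils in the intervention group were better off at both waves. If the analyst instead turns to another coefficient, the choice of coefficient, time point and coding is made without a stated rule, possibly after the data have been seen.

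**Working it through.** **1. What the interaction estimates.** Let d be the group difference in an attitude score at one week, and f the fraction of it kept at three months. With these two waves only:

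interaction = (difference at three months) − (difference at one week) = fd − d = (f − 1)d.

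- f = 1 (fully sustained): 0, whatever the size of d.
- f = 0.5, d = 0.2: −0.10.
- f = 0 (gone by three months), d = 0.2: −0.20.

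This is algebra and needs no assumed figure. For contrast, an outcome with a pretest and differences of 0, 0.2 and 0.2 at the three waves has a linear slope difference of (0.2 − 0)/2 = 0.10 per wave. The named test does pick up an intake effect.

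**2. Inputs for an illustration.**

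- From Methodology, Sample: effect size 0.2 (read as a standardised mean difference), 500 pupils, 5% level (taken as two-sided).
- From the Budget: about 30 classrooms, so m = 500/30 = 16.67 pupils each.
- Assumed, not in the documents: wave correlation r from 0.3 to 0.7, classroom ICC from 0 to 0.05, a classroom effect that is the same at both waves, total variance 1.

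The figure of 500 is used only as an input. The standard two-group formula for 0.2, power 0.8 and a 5% level gives 786 in total two-sided or 620 one-sided, so it does not reproduce 500. The present point does not depend on that.

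**3. Averaged group difference, sustained effect (f = 1, d = 0.2).**

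SE = √[(4/500) × ((1 + r)/2 + (m − 1) × ICC)]

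| r | ICC | SE | Power (normal approximation) |
|---|---|---|---|
| 0.3 | 0 | √(0.008 × 0.650) = 0.0721 | 0.79 |
| 0.3 | 0.05 | √(0.008 × 1.433) = 0.1071 | 0.46 |
| 0.5 | 0 | √(0.008 × 0.750) = 0.0775 | 0.73 |
| 0.5 | 0.05 | √(0.008 × 1.533) = 0.1108 | 0.44 |
| 0.7 | 0 | √(0.008 × 0.850) = 0.0825 | 0.68 |
| 0.7 | 0.05 | √(0.008 × 1.633) = 0.1143 | 0.42 |

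A t reference with 28 degrees of freedom (30 classrooms less 2) lowers these a little, to 0.76 at the top and 0.39 at the bottom.

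**4. Posttest difference alone.** SE = √[(4/500) × (1 + (m − 1) × ICC)] = 0.0894 at ICC 0 and 0.1194 at ICC 0.05. Power is 0.61 and 0.39.

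**5. Interaction.** The stable classroom effect cancels, so SE = √[(4/500) × 2(1 − r)] = 0.1058, 0.0894 and 0.0693 for r = 0.3, 0.5 and 0.7.

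- f = 1: the expectation is 0, so the rejection rate is 0.05 at every r, for any d and any sample size.
- f = 0.5: the expectation is −0.10. The test is significant with probability 0.16, 0.20 and 0.30 for the three values of r. The chance that it is significant in the intervention's favour is largest at r = 0.3, where it is P(Z < −1.96 − 0.10/0.1058) = P(Z < −2.905) = 0.0018.

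**6. Simulation check.** With classroom means, 30 classrooms of 17, r = 0.5 and an assumed ICC of 0.03 (4,000 runs), a constant effect of 0.2 made the interaction significant in 5.8% of runs and the averaged group difference in 49%. With a constant effect of 0.4 the figures were 4.9% and 97%.

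**The case against.** **Attitudes may have a pretest.** The timing phrase directly follows the mention of intervention sessions, so the sentence is loosely built, and a slope of change fits an outcome with a baseline better. This stands as a reason for caution. But the documents describe no sessions at the posttest or at three months, the same paragraph gives intake a pretest and does not give attitudes one, and nothing elsewhere assigns attitudes to the pretest. Post-only is the more natural reading, not a certain one.

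**The interaction may be meant for intake only.** Intake is the only example given at level one. It is introduced as an example, however, and the test is stated for the dependent variables in general. If intake alone is meant, nothing is mis-tested, but objective 3 then has no named test, and the same added sentence closes that gap.

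**The planned models already contain the answer.** A reader might infer from the mismatch that the trial cannot answer objective 3. The documents do not support that. Assigned intervention is a level-two variable, and a model with intervention × time would ordinarily also carry the intervention coefficient. With time 0 at posttest, that coefficient is the posttest group difference. The mediation model also needs a path from intervention to attitude, although it is stated only for mediation and without saying whether classrooms are accounted for. The fault is in the named test, not in the data or the model family.

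**Time coding may hardly matter.** A reader might infer that the intervention coefficient would be badly distorted. With attitude waves coded 1 and 2 and pretest 0, it equals (2 − f)d, or 0.30 instead of 0.20 at f = 0.5. Coded in weeks, about 1 and 13, it is 0.2 + 0.1/12 = 0.208. At f = 1 either coding gives 0.20. The documents state no coding, so no particular distortion can be claimed, only that the coefficient's meaning is not fixed.

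**Conclusion.** The point holds, conditional on post-only attitude measurement, which is the natural reading and is not rebutted elsewhere. Under it, the only effect test named for the dependent variables has expectation (f − 1)d for attitudes: zero for a fully sustained benefit and negative for a partly fading one. That part rests on no assumed figure.

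In the illustration, a sustained effect of 0.2 SD is detected with power of about 0.4 to 0.8 by the averaged group difference and 0.05 by the interaction. The first range depends on the assumed correlation, ICC and stable classroom effect, and it ignores the balancing of allocation within school and grade. The 0.05 does not depend on the assumed values.

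The consequence is limited. Intake has a pretest and its analysis is not affected. A reader might infer that the missing attitude baseline invalidates the comparison of groups. It does not: under randomisation the post-intervention difference is a valid comparison, only without baseline adjustment. The named test should be corrected; the design need not change. If attitudes are in fact measured at pretest, the point falls away.

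**What to change.** In Statistical Analysis, name as the objective 3 test the intervention-versus-control difference in each attitude variable at posttest and at three months, or the average of the two, with classroom clustering accounted for. Either treat time as a category, or state a coding with 0 at posttest and say which coefficient is the test. For these two outcomes, keep intervention × time only to describe persistence.

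In Measurements, state at which waves the attitude scales are given.

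The cost is a sentence or two in the analysis text and a clarifying phrase in Measurements, written before the outcome data are examined. No new participants, waves or questionnaire items are needed.
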